10.5.4 Overall Adaptive Design Performance

Finally, the Cui/Hung/Wang (CHW) approach is compared to the Chen/DeMets/Lan (CDL) approach without pre-defined fixed weights for the final analysis (which is valid as sample size may only be increased if CP (obtained under observed trend) at the second interim analysis exceeds 50%).

All the results below are for the group-sequential design with adaptive sample size re-estimation procedure as described in previous sections and based on 10.000 simulated trials each.

Scenario 1: true progression probabilities are 30% (SOC) and 15% (RESP301+SOC)

Scenario 2: true progression probabilities are 24% (SOC) and 14% (RESP301+SOC)

Scenario 3: true progression probabilities are 30% (SOC) and 10% (RESP301+SOC)

Scenario 4: true progression probabilities are 24% (SOC) and 20% (RESP301+SOC)

10.6 Appendix 6: Abbreviations

AE	adverse event
ALT	alanine aminotransferase
AST	aspartate aminotransferase
CBC	complete blood count
CFR	Code of Federal Regulations
CI	Confidence interval
CIOMS	Council for International Organizations of Medical Sciences
COPD	Chronic obstructive pulmonary disease
COVID-19	Coronavirus disease 2019
CP	Conditional power
CRF	case report form(s) (paper or electronic as appropriate for this study)
CRO	contract research organization
CV	cardiovascular
DMC	Data Monitoring Committee
DRE	disease-related events
ECG	electrocardiogram
ECMO	Extra corporeal membrane oxygenation
EDC	electronic data capture
EoS	End of study
FDA	Food and Drug Administration
FiO ₂	fraction of inspired oxygen
FSH	follicle-stimulating hormone
GCP	Good Clinical Practice
HIPAA	Health Insurance Portability and Accountability Act
HIV	human immunodeficiency virus
HRT	hormone replacement therapy
ICF	informed consent form
ICH	International Conference on Harmonisation
IDMC	Independent Data Monitoring Committee
IEC	Independent Ethics Committee
INR	International normalized ratio
IRB	Institutional Review Board
ITT	Intent-to-treat
IVRS	interactive voice response system

IWRS	interactive web response system
LFT	Liver function test
mHb	Methemoglobin
NEWS	National Early Warning Score
NHS	National Health Service
NO	Nitric oxide
NO ₂	Nitrogen dioxide
NOx	Oxide of nitrogen
RT-PCR	Reverse transcriptase polymerase chain reaction
PP	Per protocol
PT	Prothrombin time
QTcF	QT interval corrected using Fridericia's formula
SAE	serious adverse event
SAP	statistical analysis plan
SD	Standard deviation
SoA	schedule of activities
SOC	Standard of care
SP	Safety population
SpO ₂	Oxygen saturation
SUSAR	suspected unexpected serious adverse reaction
TID	Three times daily
ULN	Upper limit of normal
US	United States
WHO	World Health Organization

11 References

ACRO, 2020

Association of clinical research organizations (ACRO). Considerations to Support Clinical Trial Monitoring Oversight During COVID-19, 13 March 2020.

Akerström S et al, 2005

Ali-Ahmad D et al, 2003

ATS/ACCP, 2003

Date and Version of Previous Protocol:

05 Jun 2020; Amendment 1 (Version 2.0)
01 May 2020; Version: 1.0

Sponsor Signatory:

PPD

10th June 2020

PPD

Date

Medical Monitor Name and Contact Information

PPD

[name]
France

Email: PPD

Protocol Amendment Summary of Changes Table

DOCUMENT HISTORY		
Document	Version	Date
Amendment 2.0	Version 3.0	10-Jun-2020
Amendment 1.0	Version 2.0	05-Jun-2020
Original Protocol	Version 1.0	01-May-2020

Amendment 2.0 (10-Jun-2020)

This amendment is considered to be substantial based on the criteria set forth in Article 10(a) of Directive 2001/20/EC of the European Parliament and the Council of the EU.

Overall Rationale for the Amendment:

The protocol was updated to clarify that staggered dosing is required for all participants treated before completion of the first Independent Data Monitoring Committee (IDMC) review, and to clarify exclusionary criteria and monitoring of methemoglobin (mHb). Information was added to ensure that investigators are aware of the potential risk of interaction between nitric oxide (NO) and other NO donor agents. Other changes, with brief rationale, are summarized in the following table.

Section # and Name	Description of Change	Brief Rationale
Section 1.3 Schedule of Activities (SoA)	Footnote 4 updated to include mHb assessment at the same time points as hematology and clinical chemistry assessments.	For monitoring and assessment of mHb against the discontinuation criteria.
Section 2.2.1 Risk Assessment	Table 2-1 updated to include exclusionary mHb >1%.	The normal reference range for mHb is 0-1% (Longo et al, 2011).
Section 5.3 Exclusion criteria	Exclusion criterion 13 updated to specify that mHb >1% is exclusionary.	

Section # and Name	Description of Change	Brief Rationale
Section 4.1 Overall Design Section 6.1 Study Intervention Administered Section 9.6 Data Monitoring Committee (DMC)	
Due to the urgency of the pandemic, if participants become eligible for the study during the IDMC review of the first 10 participants then they may be recruited. However, their administration of RESP301 will be staggered in the same way as for the first 10 participants.
 
Once the IDMC review has been completed, and provided there are no safety concerns, further recruitment will continue as per protocol. The Sponsor and contract research organization (CRO) confirm that the report from the IDMC will be sent in a timely manner to all participating sites and investigators.
	The staggered dosing approach will be used for all participants enrolled up to completion of the first IDMC safety review, to ensure appropriate safety procedures are in place for the first participants recruited into the study.
Section 6.5.1 Potential Drug Interactions	A new section was added to describe NO donor agents that may increase the risk of developing methemoglobinemia.	To ensure that investigators are aware of the potential risk of interaction between NO and other NO donor agents.
Section 7.1 Permanent Discontinuation of Study Intervention	Addition of Hy's law discontinuation criteria to the first bullet.	To ensure consistency with Appendix 10.3.
Whole document	Minor language and format changes.	For improved clarity and readability.

Table of Contents

Protocol Amendment Summary of Changes Table	3
Table of Contents	5
1 Protocol Summary	9
1.1 Synopsis.....	9
1.2 Schema	12
1.3 Schedule of Activities (SoA).....	13
2 Introduction.....	18
2.1 Background.....	18
2.2 Benefit/Risk Assessment	21
2.2.1 Risk Assessment	21
2.2.2 Benefit Assessment.....	24
2.2.3 Overall Benefit: Risk Conclusion.....	26
3 Objectives and Endpoints	26
4 Study Design.....	27
4.1 Overall Design.....	27
4.2 Scientific Rationale for Study Design	29
4.3 Justification for Dose.....	30
4.4 End of Study Definition.....	30
5 Study Population.....	30
5.1 Study Rationale	30
5.2 Inclusion Criteria	31
5.3 Exclusion Criteria.....	32
5.4 Lifestyle Considerations	33
5.5 Screen Failures	33
5.5.1 Screening and Enrollment Log and Participant Identification Numbers.....	33
6 Study Intervention	34
6.1 Study Intervention Administered.....	34
6.1.1 Medical Devices	35
6.1.2 Device Training	36

6.2	Preparation, Handling, Storage, and Accountability	36
6.2.1	Preparation of Study Intervention Product	36

1.1 Synopsis

Protocol Title: An open-label, adaptive randomized, controlled multicenter study to evaluate the efficacy and safety of RESP301 plus standard of care (SOC) compared to SOC alone in hospitalized participants with COVID-19 requiring supplemental oxygen (NOCoV2)

Sponsor Protocol No.: RESP301-002

Study Phase: Phase 2/Phase 3

Sponsor: Thirty Respiratory Limited

Rationale:

This is an open-label, randomized, multicenter, parallel group, concurrent, controlled study using a sequential adaptive design. Participants will be consented and randomized 2:1 to the Investigational arm or the Control arm. Participants randomized to the Investigational arm will receive inhaled RESP301 (6 mL) administered using a nebulizer 3 times a day (TID) for up to 10 days in addition to the standard of care (SOC) while participants in the Control arm will receive SOC alone.

Objectives and Endpoints:

Objectives	Endpoints
Primary	

To evaluate efficacy of RESP301 in preventing progression of hospitalized COVID-19 participants at level 4 in the modified World Health Organization (WHO) ordinal scale into levels >4	
Proportion of participants who progress to level >4 of modified WHO ordinal scale due to COVID-19 by Day 14
Key Secondary	

To assess the effect of RESP301 as measured by room air SpO2	
Change in room air SpO2 from baseline over time

To assess the effect of RESP301 as measured by the National Early Warning Score (NEWS) 2 symptom score	
Change in NEWS 2 symptom score from baseline over time

Objectives	Endpoints

• To assess the treatment response on clinical status	
• Change from baseline on the modified WHO ordinal scale at each visit up to Day 28• Time to improvement to a lower level (<4) of modified WHO ordinal scale• Time to progression to a higher level (>4) of modified WHO ordinal scale
Additional Secondary	

• To assess the treatment response on clinical status	
• Time to hospital discharge• Incidence of mortality by Day 28
Safety	

• To assess the overall safety profile of RESP301 in COVID-19 participants	
• Clinical safety laboratory measurements• Physical examinations• Vital signs• Concomitant medications• Counts and cumulative incidence of:
○ Adverse events (AEs)○ Serious adverse events (SAEs)○ Severe AEs

• To assess the ability of participants to tolerate nebulization	
• Incidence of participants unable to tolerate nebulization due to:
○ Reduction in SpO2 to < 90%, unless well clinically tolerated according to Investigator's opinion○ Other clinical signs of intolerance according to Investigator's opinion• Incidence of clinical bronchial hyper-responsiveness related to nebulization
Exploratory	

• CCI	
• CCI

Overall Design:

- Open-label, randomized, multicenter, parallel group, concurrent, controlled study using a sequential adaptive design to evaluate the efficacy and safety of RESP301 added to standard of care (SOC) in hospitalized patients with COVID-19 requiring supplemental oxygen.
- Participants will be stratified by country and presence of risk factors for severe outcomes of COVID-19, based on comorbidities and age as detailed in Section 6.3.
- The study treatment will be permanently discontinued prior to 10 days if the participant:
 - Improves to level 1 or 2 of the modified WHO ordinal scale;
 - Progresses to a level > 4 of the modified WHO ordinal scale;
 - Experiences an event that requires permanent discontinuation as described in Section 7.1.
- An Independent Data Monitoring Committee (IDMC) will be responsible for closely reviewing the safety and efficacy data from interim analyses and for providing their recommendations on continuation of the study. The IDMC will meet after 10, 20, 60 and 150 participants have completed the study (see Sections 9.5 and 9.6).
- A staggered dosing approach will be used for the first 10 participants (up to the first IDMC safety review). Each RESP301 dose will be administered by intermittent inhalation to monitor the tolerability and response to RESP301 (see Sections 6.1 and 9.6).

Disclosure Statement: This is a parallel group treatment study with two arms that are open-label.

Number of Participants:

Approximately 300 adult (male or female) participants will be randomly assigned to study intervention (200 to the Investigational arm and 100 to the Control arm).

Intervention Groups and Duration:

The total study duration for a participant from screening to last follow up will be up to 30 days (± 2 days). The study will be divided into the following periods:

[figure not shown]
- Screening period: starts up to 2 days (48 hours) prior to and extends up to the day of treatment initiation (Day 1); Days -2, -1 and 1
- Intervention period: up to 10 days; Day 1 to Day 10
- Efficacy follow-up: Day 14 and Day 28 (both ± 2 days)
- Safety follow-up: 28 days after treatment initiation; with the participant being contacted by phone call, if not still hospitalized, on Day 28 (± 2 days)

Participants will be consented and randomized 2:1 to the Investigational arm or the Control arm. Participants randomized to the Investigational arm will receive inhaled RESP301 (6 mL) administered using a nebulizer TID for up to 10 days in addition to the SOC, while participants in the Control arm will receive SOC alone.

Data Monitoring Committee: Yes

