4.1 Overall Design

This is an open-label, randomized, multicenter, parallel group, concurrent, controlled study in hospitalized participants with COVID-19 requiring supplemental oxygen (WHO ordinary scale level 4) using a sequential adaptive design to evaluate the efficacy and safety of RESP301 added to standard of care (SOC). Approximately 300 adult (male and female) participants will be consented and randomized 2:1 to the Investigational arm or the Control arm. Participants randomized to the Investigational arm will receive inhaled RESP301 (6 mL) administered using a vibrating mesh nebulizer TID for up to 10 days in addition to the standard of care (SOC) while participants in the Control arm will receive SOC alone.

The study will be divided into the following periods:

- Screening period: starts up to 2 days (48 hours) prior to and extends up to the day of treatment initiation (Day 1); Days -2, -1 and 1
- Intervention period: up to 10 days; Day 1 to Day 10
- Efficacy follow-up: Day 14 and Day 28 (± 2 days)
- Safety follow-up: 28 days after treatment initiation; with the participant being contacted by phone call, if not still hospitalized, on Day 28 (± 2 days)

After screening, eligible participants will be randomized to either RESP301+SOC or SOC alone on Day 1, and the study treatment will be initiated as applicable (Table 1-1). Screening and randomization may happen on the same day (Day 1).

An individual administration of study intervention will be stopped, and supplemental oxygen resumed, if threshold limits of SpO₂ 89% or heart rate 120 beats/min (or as indicated by the Investigator) are exceeded (see Section 4.2 and Section 8.1.2). However, the participant may continue with subsequent doses if the Investigator judges that the benefit / risk ratio remains positive. In this case, the instruction to continue should be duly recorded in the participant's hospital file and the subsequent nebulization should be closely monitored. Inhalation of study intervention should be completed within 20 minutes. A staggered dosing approach will be used for the first 10 participants (up to the first Independent Data Monitoring Committee [IDMC] safety review) to monitor tolerability and response to RESP301 (see Sections 6.1 and 9.6).

The study treatment will be permanently discontinued prior to 10 days if the participant:

- Improves to level 1 or 2 of the modified WHO ordinal scale;
- Progresses to a level > 4 of the modified WHO ordinal scale;

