9.4.2 Primary Endpoint

The primary endpoint is the proportion of participants who progress to level >4 of the modified WHO ordinal scale due to COVID-19 by Day 14.

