9.4.3 Secondary Endpoint(s)

The key secondary endpoints are:

1. Change from baseline on the modified WHO ordinal scale at each visit up to Day 28
2. Change in room air SpO₂ from baseline over time
3. Change in NEWS 2 symptom score from baseline over time
4. Time to improvement to a lower level (<4) of the modified WHO ordinal scale
5. Time to progression to a higher level (>4) of the modified WHO ordinal scale

Additional secondary endpoints are:

1. Time to hospital discharge
2. Incidence of mortality by Day 28

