9.5 Interim Analyses

Two interim analyses will be performed.

1. The first analysis will be conducted when about 60 participants (40 participants in the RESP301+SOC arm and 20 participants in the SOC arm) have completed the Day 10 assessment. The purpose of this analysis is to evaluate efficacy of RESP301 with the application of a futility criterion based on the results on SpO₂ change from baseline on Day 10. The following futility criterion will be used for this first interim analysis:

If the difference in the percentage of participants with at least a 2% improvement in SpO₂ between both treatment arms is less than 5%, benefit of RESP301 treatment is not expected. For a final decision to stop the study for futility the results on other endpoints will be considered as well.

As no other modification of the study at the time of the first interim analysis is considered, no adjustment of the alpha level is required.

2. The second interim analysis will be conducted after 150 participants (100 participants in the RESP301+SOC arm and 50 participants in the SOC arm) have completed the Day 14 assessment. The purpose of this analysis is the assessment of futility or a sample size re-estimation in case the actual results differ from the original assumptions for the power calculations of the study, related to the percentage of participants meeting the primary endpoint in the control arm and/or the relative treatment benefit achieved in the RESP301+SOC arm compared to the SOC arm.

To account for the multiple testing due to the second interim analysis an adjustment for the type I error alpha will be applied using the Haybittle-Peto approach which would spend one sided alpha=0.0005 at the second interim analysis and leave one-sided nominal alpha of 0.0249 for the final analysis. The futility criterion for the second interim analysis will be based on the conditional power (CP) for the final results based on the assumption that the remainder of the study will follow the same trend as observed in the interim analysis. If CP at the time of the second interim analysis is less than 20% consideration

will be given to stop the study for futility. At the same time sample size re-estimation will be performed to achieve 80% power at the end of the study. The methodology for the adjustment and the procedure to maintain the type I error level will be described in greater detail in the SAP.

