10.5 Appendix 5: Statistical Design Considerations

10.5.1 Some General Design Considerations

1. Binary primary endpoint: progression to critical stage/death up to Day 14
 - to be analyzed by a Cochran-Mantel-Haenszel (CMH) stratified for the factors used in the stratified randomization
 - subjects who withdraw from study treatment will be followed up until their primary endpoint outcome is known (i.e., up to Day 14 or progression to critical stage/death, whatever is first)
 - it is, therefore, not clear what current protocol synopsis text could mean: *If subjects are discharged from the hospital prior to day 14 due to improvement of the clinical status and their status on day 14 cannot be obtained, their status on day 14 for the primary endpoint will be imputed with the status on the day of discharge. and what the implications on statistical study characteristics could be. Further discussion is needed.*
2. Timing of the two planned interim analyses with stopping options is stated as

There are 2 interim analyses planned, the first interim analysis after the first 60 participants have completed day 10 of the observation period ... and a second interim analysis after 150 participants have completed day 14 of the observation period.

With the current text for the timing of the first interim analysis, it is not clear how many subjects will have been randomized at least 14 days prior to the interim data cut-off date and can therefore provide data for the binary primary endpoint (“progression to critical stage/death up to Day 14”).

For such a binary endpoint, Parexel does not recommend including any participant randomized less than 14 days prior to the interim data cut-off date (note this would be different to a study with a time-to-event endpoint) as

- for such participants not yet progressed, the outcome up to Day 14 is unknown and should not be imputed as “not progressed up to Day 14”
- for such participants progressed prior to Day 14, the outcome is known but their inclusion would bias the estimation of progression probability up to Day 14 in a upwards direction.

In order to set up the adaptive group-sequential study design, the following assumptions have been used:

- first interim analysis: a total of ≈ 39 participants randomized at least 14 days prior to data cut-off date
- second interim analysis: a total of $\approx 50\%$ of the initially planned number of participants randomized at least 14 days prior to data cut-off date.

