1.3 Schedule of Activities (SoA)

Table 1-1 Schedule of Activities (SoA)

Procedure	Screening (up to 48 hours before Day 1 ¹)	Intervention Period			Early withdrawal	Efficacy follow-up (Day 14) ² (± 2 days)	EoS efficacy and safety follow-up (Day 28) ² (± 2 days)	Notes
		Day 1 ¹	Daily while hospitalized	Day 10 / hospital discharge				
Informed consent	X							Optional tokenization ICF to be provided for a subset of participants in the United States (see Section 8.4)
Confirmation of COVID-19 infection by nasopharyngeal RT-PCR ³	X							
Inclusion and exclusion criteria	X	X						Recheck clinical status before 1st dose of study intervention
Demographics	X							
Physical examination including height and weight	X			X	X		X ²	Full physical exam and height only at screening

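### The ±2-day windows let the Day 14 and Day 28 contacts take place on Day 12 and Day 26, so events late in the endpoint periods can go unrecorded

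*Protocol*

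**What the plan says.** The Version 3.0 synopsis (Section 1.1, duration paragraph) gives "Efficacy follow-up: Day 14 and Day 28 (both ± 2 days"), and the closing safety contact has the participant "contacted by phone call, if not still hospitalized, on Day 28 (± 2 days"). The column header of Table 1-1 in the same version reads "Efficacy follow-up (Day 14) ² (± 2 days"), with the same tolerance for Day 28. Section 4.1, visible only in its Version 2.0 text, agrees: "Efficacy follow-up: Day 14 and Day 28 (± 2 days").

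The endpoints are cumulative. Section 9.4.2 takes the proportion who "progress to level >4 of the modified WHO ordinal scale due to COVID-19 by Day 14", and Section 9.4.3 lists "Incidence of mortality by Day 28".

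Section 8.1.1 has the ordinal scale record the level held when the assessment is made. Table 1-1 places daily scoring under the intervention period, which the synopsis defines as Days 1 to 10. After that, the scale is scheduled only at the Day 14 and Day 28 contacts.

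For the second interim analysis, Section 9.5 waits until 150 participants "have completed the Day 14 assessment". Section 9.2 instead refers to Day 14 after randomization. In Section 10.5.1 (Appendix 5) the contract research organization "does not recommend including any participant randomized less than 14 days prior to the interim data cut-off date", and it bases the design on about half the planned participants being at least 14 days past randomization.

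**The concern.** A symmetric window suits a measurement taken near a nominal day. It fits an endpoint of the form *event by Day X* badly, because an early reading closes the record before the period ends. Here a site can follow the schedule exactly and still hold no information on Days 13-14 or Days 27-28.

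At stake are the primary endpoint and the 28-day mortality endpoint. The trial is open-label and patients on active drug are handled differently from controls, so the timing of contacts could differ between arms. Unequal timing would bias the comparison, not merely dilute it. The second interim analysis, which decides futility and sample size, uses the same primary outcome data. Information that was never collected cannot be restored by a rule in an analysis plan.

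**Working it through.** **1. What an early contact leaves uncovered**

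| Event | Contact made on | Later scheduled capture |
|---|---|---|
| Death, Day 13-14 | Day 12 | Day 28 contact |
| Non-fatal level 5-6 on Day 13-14, resolved before Day 28 | Day 12 | None on the scale |
| Death, Day 27-28 | Day 26 | None |

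None of the other rules closes these gaps with certainty:
- The imputation rule in 9.4.1 applies only when Day 14 status cannot be obtained; a Day 12 contact inside the window counts as obtained.
- Follow-up until the outcome is known (10.5.1) is written for those who withdraw from study treatment.
- AE/SAE collection ends at the last follow-up visit (8.3.1). Section 10.4.2 gives death from disease progression as an example of what cannot be an SAE.

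**2. The plan's own figure**

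Inputs from 9.2: 30% versus 15%, 100 control and 200 active, one-sided alpha 0.025. Expected events = 100×0.30 + 200×0.15 = 60.
- SE under the null (pooled rate 60/300 = 0.20) = √(0.20×0.80×(1/100+1/200)) = 0.0490.
- SE under the alternative = √(0.30×0.70/100 + 0.15×0.85/200) = 0.0523.
- Pooled power = Φ[(0.15 − 1.96×0.0490)/0.0523] = 84.9%.
- Unpooled power = Φ[0.15/0.0523 − 1.96] = 81.8%.
- Continuity-corrected power (subtract ½(1/100+1/200) = 0.0075 from 0.15 in the pooled formula) = 81.3%.

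The stated approximately 80% is reproduced by the last two. The continuity-corrected sample size for 80% power is 291, close to the planned 300.

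**3. Everyone read on Day 12 (upper bound)**

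The documents give no event timing. Assumption: Weibull time to progression scaled to the planned Day 14 rates, so risk at day d = 1 − (1−p)^((d/14)^k). Here k = 1 is constant hazard, and k = 0.7 and 0.5 are increasingly front-loaded. Example, k = 1: 1 − 0.70^(12/14) = 26.3%; 1 − 0.85^(12/14) = 13.0%.

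| k | Control | Active | Missed of 60 | Power: pooled | unpooled | continuity-corrected |
|---|---|---|---|---|---|---|
| 1 | 26.3% | 13.0% | 7.7 | 80.1% | 75.9% | 75.6% |
| 0.7 | 27.4% | 13.6% | 5.5 | 81.6% | 77.8% | 77.4% |
| 0.5 | 28.1% | 14.0% | 3.9 | 82.6% | 78.9% | 78.5% |

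The loss is about 2 to 6 percentage points of power, depending on formula and shape. If only a quarter of contacts came two days early (assumption), the control rate with k = 1 would fall by 0.25×3.7 = 0.9 points.

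**4. Unequal timing, no drug effect**

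Both true rates 30%, all of the active arm read on Day 12 and all controls on Day 14. With k = 1, the apparent difference is 30.0 − 26.3 = 3.7 points. Pooled one-sided rejection is about 10%, 7% and 5% for k = 1, 0.7 and 0.5, against a nominal 2.5%. This is an extreme.

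**5. Mortality read on Day 26**

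Same model over 28 days, with assumed 28-day mortality of 5% to 20%. Example, k = 1 and 10%: 1 − 0.90^(26/28) = 9.32%, so 6.8% of deaths are missed. Across the range, about 3% to 7%.

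**The case against.** The strongest reply is that little would really be lost. Levels 5 and 6 exist only in hospital, so an escalation leaves a dated chart entry. A death on Day 13 or 14 surfaces at the Day 28 contact. SAEs are reportable up to 18 days after the last dose (10.4.4), which reaches Day 28 for someone dosed to Day 10. Even with everyone read two days early, the pooled formula keeps power at 80%, and nothing in the documents says that one arm would be contacted earlier.

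Much of this stands. But no passage shown tells sites to go back to the chart after an early contact. The 18-day rule cannot apply to controls, who receive no dose, and does not reach deaths from progression. The figures above are rightly read as ceilings.

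Three stronger readings are tempting and should not be drawn:
- *Events are lost.* They can be; records may recover some.
- *Escalations on Day 15 or 16 are necessarily counted as Day 14 events.* Time to progression is a key secondary endpoint analysed by Cox model and Kaplan-Meier curves (9.4.1, 9.4.3), so progression times are needed. Counting by date could belong in an analysis plan that is not shown.
- *The interim rule contradicts Appendix 5 in substance.* Randomization is on Day 1, so a Day 12 contact is only 11 days after it, and 9.5 taken alone would admit it. However, 9.2 and 10.5.1 already use elapsed time since randomization, so this is loose wording in 9.5.

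**Conclusion.** The concern holds in a limited form. The schedule permits contacts before the endpoint periods end, and events after an early contact can then escape scheduled ascertainment. The Day 28 side is the clearer one, since no contact follows it. The Day 14 side is confined to non-fatal escalations that resolve before Day 28.

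With balanced timing the effect is modest: at most about 4 to 8 of 60 primary events and about 3% to 7% of deaths, with every participant read at the early edge and nothing recovered. These figures rest on an assumed event-time shape and, for deaths, an assumed mortality rate. Arm-dependent timing would matter more; the documents make it possible without showing that it is likely. The sample size needs no change.

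Confidence is moderate. The windows are confirmed in the Version 3.0 synopsis and Table 1-1 header. Most Version 3.0 text beyond that header is not shown, so the remaining points rest on Version 2.0 text; the Amendment 2 change table reports no change to these provisions.

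**What to change.** 1. In the synopsis, Table 1-1 and Section 4.1, make both windows one-sided: Day 14, 0 to +2 days; Day 28, 0 to +2 days.
2. At each contact, record the date of any escalation to level >4 and the date of any death since the last assessment. Count for the endpoints only events dated on or before Day 14 or Day 28. The one-sided window prevents early closure; the dates keep later contacts from adding later events.
3. Reword the second-interim trigger in Section 9.5 to elapsed time since randomization, matching Section 9.2 and Appendix 5.

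The cost is amendment wording and one or two date fields. Sites give up the option of an early contact, and contacts that would have been made early move to the nominal day or up to two days after it. No visits are added.
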